2. BACKGROUND

2.1 Study Disease

Chondrosarcoma is the second most common primary malignancy of bone after osteosarcoma and is characterized by the production of cartilage matrix by the tumor cells ([Fletcher et al., 2002](#)). Several categories of primary chondrosarcomas have been described, including conventional, dedifferentiated, mesenchymal, and clear cell chondrosarcoma.

Conventional chondrosarcomas represent approximately 85% of all chondrosarcomas and can be categorized according to their location in bone into primary central and secondary peripheral chondrosarcomas. Central and peripheral chondrosarcomas are histologically similar, and for both, three different grades are described, which represent the best predictor of outcome. Grade I chondrosarcomas are poorly cellular, with an abundant hyaline cartilage matrix, and rarely metastasize. In contrast, grade III chondrosarcomas are highly cellular, with a mucomyxoid

matrix and mitoses, and metastasize in about 70% of cases ([Evans et al., 1977](#); [Fletcher et al., 2002](#)). The most frequent metastatic sites are the lungs, regional lymph nodes and liver. Up to 13% of recurrent chondrosarcomas exhibit a higher grade of malignancy than the original lesion, suggesting chondrosarcomas may biologically progress.

Dedifferentiated chondrosarcoma represent 9%–10% of all chondrosarcomas and is characterized from a histological point of view by conventional low-grade chondrosarcoma with abrupt transition to foci that have dedifferentiated into a higher-grade, more aggressive component ([Fletcher et al., 2002](#)). Patients with dedifferentiated chondrosarcoma are older than those with conventional lesions; the median age at diagnosis is 60 years. The prognosis is poor. Indeed, metastases occur early, are frequent and involves typically the lungs, regional lymph nodes and viscera ([Mercuri et al., 1995](#)). The 5-year survival rate is less than 10%–25%.

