Mesenchymal chondrosarcoma represent 2%–13% of all chondrosarcomas and is characterized by a typical bimorphic appearance with a malignant cartilaginous component admixed with a more cellular vascular portion with hemangiopericytoma-like features ([Fletcher et al., 2002](#)). Patients with mesenchymal chondrosarcoma are younger than those with conventional lesions; the median age at diagnosis is 25 years. Local and distant recurrences are frequent. The most frequent metastatic sites are the lungs, regional lymph nodes and bone. Patients with intraosseous lesions have a 5-year survival rate of 42% and a 10-year survival rate of 28% ([Nakashima et al., 1986](#)). Patients with extraskeletal mesenchymal chondrosarcoma have an estimated survival rate of 55% at 5 years and 27% at 10 years.

Clear cell chondrosarcoma is a rare low-grade malignant cartilaginous tumor representing 1-2% of all chondrosarcomas ([Fletcher et al., 2002](#)). These tumors consist in a proliferation of large cells with abundant clear, vacuolated cytoplasm containing large amounts of glycogen (clear cell chondrocytes) that often lie between heavily calcified trabeculae of cartilage matrix and may superficially resemble bone. Patients are most commonly affected in the 3rd to 5th decade of life. Metastases are rare. However, clear cell chondrosarcoma is often confounded with chondroblastoma due to its epiphyseal location. Therefore, clear cell chondrosarcoma is often inadequately treated initially with curettage leading to recurrence. Overall recurrence rate is 16% and approximately 15% of patients die of the disease ([Unni et al., 1976](#)).

In the majority of cases, patients with chondrosarcomas (especially those with conventional or clear cell chondrosarcoma) are cured by adequate wide surgical excision. However, some patients (especially those with high grade conventional, mesenchymal or dedifferentiated chondrosarcomas) present or recur with metastatic disease. Conventional cytotoxic agents and radiotherapy are generally not effective in patients with metastatic or locally unresectable disease ([Gelderblom et al., 2008](#)). Therefore, there is an urgent need to develop new therapeutic strategies for patients with advanced disease.

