3. PATIENT SELECTION

3.1 Eligibility Criteria

- 3.1.1 Patients must have histologically confirmed diagnosis of chondrosarcoma (conventional, mesenchymal, dedifferentiated or clear cell subtypes).
- 3.1.2 Patients must have measurable disease (outside any previously irradiated field) defined as at least one lesion that can be accurately measured in at least one dimension (longest diameter to be recorded) as ≥ 10 mm with spiral CT scan. [See Section 11](#) for the evaluation of measurable disease.
- 3.1.3 No more than three prior lines of chemotherapy for advanced disease (including no more than 450 mg/m² doxorubicin). At least three weeks since last chemotherapy (six weeks in case of nitrosoureas and mitomycin C), immunotherapy or any other pharmacological treatment and/or radiotherapy.
- 3.1.4 Age ≥ 18 years (Because only limited adverse event data are currently available on the use of GCD-0449 in patients < 18 years of age, children are excluded from this study but will be eligible for future pediatric phase 2 combination trials).
- 3.1.5 Life expectancy of greater than 3 months
- 3.1.6 ECOG performance status ≤ 2 (Karnofsky $\geq 60\%$; see [Appendix A](#)).
- 3.1.7 Patients must have normal organ and marrow function as defined below:
 - a. leukocytes $\geq 3,000/\text{mcL}$
 - b. absolute neutrophil count $\geq 1,500/\text{mcL}$
 - c. platelets $\geq 100,000/\text{mcL}$
 - d. total bilirubin within normal institutional limits
 - e. AST(SGOT)/ALT(SGPT) ≤ 2.5 X institutional upper limit of normal
 - f. Creatinine within normal institutional limitsOR
creatinine clearance > 60 mL/min/1.73 m² for patients with creatinine levels above institutional normal
- 3.1.8 Metastatic or unresectable locally advanced disease.
- 3.1.9 Documented disease progression (as per RECIST) before study entry.
- 3.1.10 Hh pathway inhibitors such as vismodegib have been demonstrated to be embryotoxic and/or teratogenic in multiple animal species and can cause severe midline defects, missing digits, and other irreversible malformations in the developing embryo or fetus. For this reason, women of child-bearing potential and men must use two forms of contraception (i.e., barrier contraception and one other method of contraception) at least 4 weeks prior to study entry, for the duration of

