11.1.1 Definitions

Evaluable for toxicity: All patients will be evaluable for toxicity from the time of their first treatment with GDC-0449.

Evaluable for objective response: Only those patients who have measurable disease present at baseline and have received at least one complete or two incomplete cycle of therapy will be included in the main analysis of the response rate.

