11.1.2 Disease Parameters

Measurable disease. Measurable lesions are defined as those that can be accurately measured in at least one dimension (longest diameter to be recorded) as ≥ 20 mm by chest x-ray, as ≥ 10 mm with CT scan, or ≥ 10 mm with calipers by clinical exam. All tumor measurements must be recorded in millimeters (or decimal fractions of centimeters).

Note: Tumor lesions that are situated in a previously irradiated area are not considered measurable.

Malignant lymph nodes. To be considered pathologically enlarged and measurable, a lymph node must be ≥ 15 mm in short axis when assessed by CT scan (CT scan slice thickness recommended to be no greater than 5 mm). At baseline and in follow-up, only the short axis will be measured and followed.

Non-measurable disease. All other lesions (or sites of disease), including small lesions (longest diameter < 10 mm or pathological lymph nodes with ≥ 10 to < 15 mm short axis), are considered non-measurable disease. Bone lesions, leptomeningeal disease, ascites, pleural/pericardial effusions, lymphangitis cutis/pulmonitis, inflammatory breast disease, and abdominal masses (not followed by CT or MRI), are considered as non-measurable.

Note: Cystic lesions that meet the criteria for radiographically defined simple cysts should not be considered as malignant lesions (neither measurable nor non-measurable) since they are, by definition, simple cysts.

‘Cystic lesions’ thought to represent cystic metastases can be considered as measurable lesions, if they meet the definition of measurability described above. However, if non-cystic lesions are present in the same patient, these are preferred for selection as target lesions.

Target lesions. All measurable lesions up to a maximum of 2 lesions per organ and 5 lesions in total, representative of all involved organs, should be identified as **target lesions** and recorded and measured at baseline. Target lesions should be selected on the basis of their size (lesions with the longest diameter), be representative of all involved organs, but in addition should be

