Patients with a global deterioration of health status requiring discontinuation of treatment without objective evidence of disease progression at that time should be reported as ‘symptomatic deterioration’. Every effort should be made to document objective progression even after discontinuation of treatment. Symptomatic deterioration is *not* a descriptor of an objective response: it is a reason for stopping study therapy. The objective response status of such patients is to be determined by evaluation of target and non-target disease as shown in Tables belows.

Table 1 – Time point response: patients with target (+/- non-target) disease.

| Target lesions | Non-target lesions | New lesions | Overall response |
|-------------------|-----------------------------|-------------|------------------|
| CR | CR | No | CR |
| CR | Non-CR/non-PD | No | PR |
| CR | Not evaluated | No | PR |
| PR | Non-PD or not all evaluated | No | PR |
| SD | Non-PD or not all evaluated | No | SD |
| Not all evaluated | Non-PD | No | NE |
| PD | Any | Yes or No | PD |
| Any | PD | Yes or No | PD |
| Any | Any | Yes | PD |

CR = complete response, PR = partial response, SD = stable disease, PD = progressive disease, and NE = inevaluable.

Table 2 – Time point response: patients with non-target disease only.

| Non-target lesions | New lesions | Overall response |
|--------------------|-------------|----------------------------|
| CR | No | CR |
| Non-CR/non-PD | No | Non-CR/non-PD ^a |
| Not all evaluated | No | NE |
| Unequivocal PD | Yes or No | PD |
| Any | Yes | PD |

CR = complete response, PD = progressive disease, and NE = inevaluable.
^a a ‘Non-CR/non-PD’ is preferred over ‘stable disease’ for non-target disease since SD is increasingly used as endpoint for assessment of efficacy in some trials so to assign this category when no lesions can be measured is not advised.

Conditions that define ‘early progression, early death and inevaluability’ are study specific and should be clearly described in each protocol (depending on treatment duration, treatment periodicity).

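### Section 11.1.2 classes every bone lesion as non-measurable in a trial of a primary bone tumour, so a patient whose only disease is a bone mass is ineligible as written or, if enrolled, has no defined 6-month outcome

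*Combined protocol and SAP*

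**What the plan says.** **Disease and eligibility.** Section 2.1 states: "Chondrosarcoma is the second most common primary malignancy of bone after osteosarcoma". Criterion 3.1.2 reads "Patients must have measurable disease (outside any previously irradiated field) defined as at least one lesion" of 10 mm or more on spiral CT, and refers to Section 11 for how measurability is judged. Criterion 3.1.8 admits "Metastatic or unresectable locally advanced disease".

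**Measurability.** Section 11.1.2 opens with a size definition: 10 mm or more on CT, with other thresholds for chest x-ray and calipers. Its paragraph on non-measurable disease then lists "Bone lesions, leptomeningeal disease, ascites, pleural/pericardial effusions" and further items. Bone lesions carry no qualifier. The only qualifier in the list, about not being followed by CT or MRI, comes directly after abdominal masses.

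**Evaluability.** Section 11.1.1 admits to the main response analysis "Only those patients who have measurable disease present at baseline" and who had the minimum treatment. Section 13.2 makes meeting the eligibility criteria a condition of being evaluable, and Section 13.5.2 applies the same condition to the main analysis.

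**Scoring.** In Section 11.1.4, Table 2 covers patients with non-target disease only. Its categories are CR, Non-CR/non-PD, NE and PD. Its footnote, on stable disease, says "to assign this category when no lesions can be measured is not advised". Section 13.1 defines success as alive at 6 months with CR, PR or SD, and failure as death or progression. Appendix JC codes non-target lesions at 6 months as CR or PD only.

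**Review.** Under Section 11.1.8 one central radiologist reviews the 6-month status against baseline, and that reading prevails over the local one.

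**The concern.** The rule on bone lesions sits badly with the disease. The protocol invites locally advanced cases of a bone tumour and then says that bone lesions cannot be measured. Pathology Form B (Appendix IB) lists nearly the whole skeleton as possible tumour sites, and Section 2.1 says grade I tumours rarely metastasize. A patient with a bone mass and nothing else is therefore a foreseeable candidate.

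Whether a bone mass can be a target lesion decides three things: who may enter, who is evaluable, and whether a patient who is stable at 6 months counts as a success. Two rules in the same section point in different directions. A site may follow the 10 mm rule and the central reviewer the bone sentence. The planned central review starts only once 6-month data exist, so a disagreement would surface after treatment.

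**Working it through.** **1. The plan's own figures (Section 13.2).** Inputs: null rate 0.20, target rate 0.40, type I error 0.10, power 0.90; stop if 3 or fewer of 17 are progression-free; positive if 11 or more of 37 are.

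P(positive | p) = Σ over x = 4 to 17 of P(X₁ = x) × P(X₂ ≥ 11 − x), with X₁ ~ Bin(17, p) and X₂ ~ Bin(20, p).

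- p = 0.20: 0.0948, within the 10% limit.
- p = 0.40: 0.9033, above the 90% requirement.
- Early stopping at p = 0.20: P(X₁ ≤ 3) = 0.549, so expected N = 17 + (1 − 0.549) × 20 = 26.0. A search over two-stage designs returns this same design as Simon-optimal.
- Recruitment: 37 × 1.2 = 44.4, rounded up to 45, as stated.

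The design arithmetic is sound. The problem lies in the definitions.

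**2. Patients traced through the text.** All are alive and without progression at 6 months.

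| Patient | Target lesion? | 3.1.2 | 6-month category | Section 13.1 |
|---|---|---|---|---|
| Bone mass plus a measurable lung, nodal or other non-bone lesion | Yes, the non-bone lesion | Met | CR, PR or SD (Table 1) | Success |
| Extraskeletal tumour of measurable size | Yes | Met | CR, PR or SD | Success |
| Bone mass only; bone sentence applied at entry | No | Not met | Not enrolled | Not applicable |
| Bone mass only; 10 mm rule applied by site and reviewer | Yes | Met | CR, PR or SD | Success |
| Bone mass only; site applies the 10 mm rule, reviewer the bone sentence | Disputed | Disputed | Non-CR/non-PD (Table 2), short of CR | Neither success nor failure |

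The last three rows are the same patient. The result depends only on which sentence of Section 11.1.2 the reader applies. In the last row the patient's place in the evaluable set is also disputed, because Sections 11.1.1, 13.2 and 13.5.2 all depend on measurable disease or eligibility. Appendix JC has no code for the category that Table 2 assigns.

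**3. What this does to the trial's numbers.**

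- If bone-only patients are screened out, all 37 evaluable patients have a target lesion. The decision rule and its power of 0.9033 stand. The cost is slower accrual and a result that does not describe bone-only disease.
- If some are enrolled and later ruled non-measurable, each takes one of the 45 − 37 = 8 places allowed for non-evaluable patients.
- The accrual cost depends on the share f of otherwise eligible candidates who are bone-only. The documents do not give f. Enrolling 45 would need 45/(1 − f) candidates. Purely as an assumption, f = 10% gives 50 and f = 40% gives 75. The planned rate of 2–3 patients a month may already allow for this; the text does not say.

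**The case against.** **The exclusion is deliberate and clear.** A general size rule followed by a specific exception is ordinary drafting, so bone lesions are simply out. This reading is available and is probably the literal one. But it shuts out part of the population that 3.1.8 admits, without saying so or giving a reason.

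**The CT/MRI qualifier covers the whole list.** If so, a bone lesion followed by CT would be measurable. The qualifier reads more naturally with abdominal masses alone; applied throughout, it would also make effusions followed by CT measurable.

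**The cited guideline may settle it.** Section 11.1 adopts RECIST 1.1. That guideline is not among the documents and is not relied on here. Section 11.1.2 states its own rule without exception, and that is the text sites will use.

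**The affected group may be small.** Section 2.1 names lungs, regional nodes and liver or viscera as the usual metastatic sites for conventional and dedifferentiated disease, and it recognises extraskeletal cases: "Patients with extraskeletal mesenchymal chondrosarcoma have an estimated survival rate". Patients with measurable disease at such sites are unaffected. This stands, and the size of the group is unknown.

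**Two stronger readings are tempting.** A reader might infer a large loss of power, by leaving bone-only patients among the 37 and counting them as non-successes. The documents do not support this: the evaluability rules keep patients without measurable disease out of the 37, and Section 13.1 reserves failure for death or progression. For the same reason no fraction of the 37 can be said to drop out, since 37 is already the evaluable number. A reader might also infer that a bone-only patient can never be scored stable. The Table 2 footnote advises against SD and does not forbid it. The text leaves a gap rather than a prohibition.

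**Conclusion.** Wrong as written. Section 11.1.2 gives a size rule and an unqualified bone exclusion that lead to different answers for a CT-measurable bone mass, in a trial of a primary bone tumour that requires measurable disease. Taken literally, bone-only patients are ineligible and outside the evaluable set. If one is enrolled under the size rule, a stable 6-month status falls into a category with no assigned primary outcome and no code on the review form.

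The size of the problem cannot be fixed from the documents, because they give no bone-only share. The effect is on accrual, on the population the result describes and on agreement between site and reviewer. The sample size and its stated power at 37 evaluable patients are not in question. A disputed classification would alter the go/no-go decision only if the count lay at a boundary: 3 or 4 of the first 17, or 10 or 11 of 37.

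The conclusion assumes that no separate imaging instruction already exempts bone masses; none appears in the documents.

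**What to change.** In Section 11.1.2, limit the exclusion to bone lesions with no component that meets the section's own size definition on CT, or on MRI where MRI is used. State that a bone primary or bone metastasis with such a component is measurable and may be a target lesion. Require sites and the central reviewer to apply this rule to the baseline scan.

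Two related entries should be brought into line. Section 13.1 should say how Non-CR/non-PD at 6 months is counted, and Appendix JC should have a code for it. The synopsis should refer to Section 11 for measurable disease, as 3.1.2 does; it now refers to Section 12, which covers data reporting.

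The cost is a short change to Section 11.1.2, a line in the reviewer's instructions and the small corrections above. The downside is that bone-mass measurements may be somewhat less reproducible. Section 11.1.2 already directs that target lesions be ones that can be measured reproducibly, which limits this.

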11.1.3 Methods for Evaluation of Measurable Disease

All measurements should be taken and recorded in metric notation using a ruler or calipers. All baseline evaluations should be performed as closely as possible to the beginning of treatment and never more than 4 weeks before the beginning of the treatment.

The same method of assessment and the same technique should be used to characterize each identified and reported lesion at baseline and during follow-up. Imaging-based evaluation is preferred to evaluation by clinical examination unless the lesion(s) being followed cannot be imaged but are assessable by clinical exam.

Conventional CT and MRI: This guideline has defined measurability of lesions on CT scan based on the assumption that CT slice thickness is 5 mm or less. If CT scans have slice thickness greater than 5 mm, the minimum size for a measurable lesion should be twice the slice thickness. MRI is also acceptable in certain situations (e.g. for body scans).

11.1.4 Response Criteria

Evaluation of Target Lesions

Complete Response (CR): Disappearance of all target lesions. Any pathological lymph nodes (whether target or non-target) must have reduction in short axis to <10 mm.

Partial Response (PR): At least a 30% decrease in the sum of the diameters of target lesions, taking as reference the baseline sum diameters.

Progressive Disease (PD): At least a 20% increase in the sum of the diameters of target lesions, taking as reference the smallest sum on study (this includes the baseline sum if that is the smallest on study). In addition to the relative increase of 20%, the sum must also demonstrate an absolute increase of at least 5 mm. (Note: the appearance of one or more new lesions is also considered progressions).

Stable Disease (SD): Neither sufficient shrinkage to qualify for PR nor sufficient increase to qualify for PD, taking as reference the smallest sum diameters while on study

Evaluation of Non-Target Lesions

Complete Response (CR): Disappearance of all non-target lesions and normalization of tumor marker level. All lymph nodes must be non-pathological in size (<10 mm short axis)

Note: If tumor markers are initially above the upper normal limit, they must normalize for a patient to be considered in complete clinical response.

Non-CR/Non-PD: Persistence of one or more non-target lesion(s) and/or maintenance of tumor marker level above the normal limits

Progressive Disease (PD): Appearance of one or more new lesions and/or unequivocal progression of existing non-target lesions.

Although a clear progression of “non-target” lesions only is exceptional, the opinion of the treating physician should prevail in such circumstances, and the progression status should be confirmed at a later time by the review panel (or Principal Investigator).

Definition of the best response

The best response determination in trial where confirmation of complete or partial response is required:

Complete or partial responses may be claimed only if the criteria for each are met at a subsequent time point as specified in the protocol (**generally 4 weeks later**). In this circumstance, the best overall response can be interpreted as in Table below.

| Table 3 – Best overall response when confirmation of CR and PR required. | | |
|--|---|---|
| Overall response First time point | Overall response Subsequent time point | BEST overall response |
| CR | CR | CR |
| CR | PR | SD, PD or PR ^a |
| CR | SD | SD provided minimum criteria for SD duration met, otherwise, PD |
| CR | PD | SD provided minimum criteria for SD duration met, otherwise, PD |
| CR | NE | SD provided minimum criteria for SD duration met, otherwise NE |
| PR | CR | PR |
| PR | PR | PR |
| PR | SD | SD |
| PR | PD | SD provided minimum criteria for SD duration met, otherwise, PD |
| PR | NE | SD provided minimum criteria for SD duration met, otherwise NE |
| NE | NE | NE |

CR = complete response, PR = partial response, SD = stable disease, PD = progressive disease, and NE = inevaluable.
^a If a CR is truly met at first time point, then any disease seen at a subsequent time point, even disease meeting PR criteria relative to baseline, makes the disease PD at that point (since disease must have reappeared after CR). Best response would depend on whether minimum duration for SD was met. However, sometimes 'CR' may be claimed when subsequent scans suggest small lesions were likely still present and in fact the patient had PR, not CR at the first time point. Under these circumstances, the original CR should be changed to PR and the best response is PR.

Special notes on response assessment

When nodal disease is included in the sum of target lesions and the nodes decrease to ‘normal’ size (<10 mm), they may still have a measurement reported on scans. This measurement should be recorded even though the nodes are normal in order not to overstate progression should it be based on increase in size of the nodes. As noted earlier, this means that patients with CR (complete response) may not have a total sum of ‘zero’ on the case report form (CRF).

In trials where confirmation of response is required, repeated ‘NE’ time point assessments may complicate best response determination. The analysis plan for the trial must address how missing data/assessments will be addressed in determination of response and progression. For example, in most trials it is reasonable to consider a patient with time point responses of PR-NE-PR as a confirmed response.

Patients with a global deterioration of health status requiring discontinuation of treatment without objective evidence of disease progression at that time should be reported as ‘symptomatic deterioration’. Every effort should be made to document objective progression even after discontinuation of treatment. Symptomatic deterioration is *not* a descriptor of an objective response: it is a reason for stopping study therapy. The objective response status of such patients is to be determined by evaluation of target and non-target disease as shown in Tables belows.

Table 1 – Time point response: patients with target (+/- non-target) disease.

| Target lesions | Non-target lesions | New lesions | Overall response |
|-------------------|-----------------------------|-------------|------------------|
| CR | CR | No | CR |
| CR | Non-CR/non-PD | No | PR |
| CR | Not evaluated | No | PR |
| PR | Non-PD or not all evaluated | No | PR |
| SD | Non-PD or not all evaluated | No | SD |
| Not all evaluated | Non-PD | No | NE |
| PD | Any | Yes or No | PD |
| Any | PD | Yes or No | PD |
| Any | Any | Yes | PD |

CR = complete response, PR = partial response, SD = stable disease, PD = progressive disease, and NE = inevaluable.

Table 2 – Time point response: patients with non-target disease only.

| Non-target lesions | New lesions | Overall response |
|--------------------|-------------|----------------------------|
| CR | No | CR |
| Non-CR/non-PD | No | Non-CR/non-PD ^a |
| Not all evaluated | No | NE |
| Unequivocal PD | Yes or No | PD |
| Any | Yes | PD |

CR = complete response, PD = progressive disease, and NE = inevaluable.
^a a ‘Non-CR/non-PD’ is preferred over ‘stable disease’ for non-target disease since SD is increasingly used as endpoint for assessment of efficacy in some trials so to assign this category when no lesions can be measured is not advised.

Conditions that define ‘early progression, early death and inevaluability’ are study specific and should be clearly described in each protocol (depending on treatment duration, treatment periodicity).

In some circumstances it may be difficult to distinguish residual disease from normal tissue. When the evaluation of complete response depends upon this determination, it is recommended that the residual lesion be investigated (fine needle aspirate/biopsy) before assigning a status of complete response. FDG-PET may be used to upgrade a response to a CR in a manner similar to a biopsy in cases where a residual radiographic abnormality is thought to represent fibrosis or scarring. The use of FDG-PET in this circumstance should be prospectively described in the protocol and supported by disease specific medical literature for the indication. However, it must be acknowledged that both approaches may lead to false positive CR due to limitations of FDG-PET and biopsy resolution/sensitivity.

For equivocal findings of progression (e.g. very small and uncertain new lesions; cystic changes or necrosis in existing lesions), treatment may continue until the scheduled assessment. If at the next scheduled assessment, progression is confirmed, the date of progression should be the earlier date when progression was suspected.

